Median (range) time to response among the 78 subjects in the talimogene laherparepvec arm with a response was 4.1 (1.2 to 16.7) months, whereas among the 8 in the GM-CSF arm with a response, it was 3.7 (1.9 to 9.1) months. Fifty-four percent of talimogene laherparepvec objective responders and 48% of talimogene laherparepvec durable responders exhibited “interval progression”, which is transient locoregional or distant progression including appearance of new lesions, before ultimately achieving response (Kaufman et al, 2013). When investigator-reported response rates (decrease in lesion area: PR, 50 to <100%; CR, 100%) of 3,916 measurable lesions (average 13) in 285 subjects treated by talimogene laherparepvec in the OPTiM Study were analyzed retrospectively, CR and PR rates in injected lesions were 47% and 17%, respectively. CR and PR in non-injected non-visceral lesions were 22% and 12%, respectively. CR and PR in visceral lesions, which were also non-injected, were 9% and 6%, respectively (Andtbacka et al, 2014).

The most common side effects in the OPTiM study were chills (talimogene laherparepvec, 49%; GM-CSF, 9%), pyrexia (43%; 9%), injection-site pain (28%; 6%), nausea (36%; 20%), influenza-like illness (30%; 15%), and fatigue (50%; 36%). Grade \geq 3 adverse events occurred in 36% of subjects receiving talimogene laherparepvec and 21% of subjects receiving GM-CSF. The only grade 3/4 adverse events occurring in \geq 5 of subjects was cellulitis (talimogene laherparepvec, n=6 [2.1%]; GM-CSF, n=1 [$<$ 1%]). Of 10 fatal adverse events in the talimogene laherparepvec arm, 8 were attributable to disease progression. The remaining 2 fatal adverse events

(sepsis in the setting of salmonella infection; myocardial infarction) were not considered treatment-related per investigator.

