When an non-index lesion splits into two or more lesions, the apparently larger lesion will be reported as a non-index lesion. All other smaller lesions will be reported as new non-index lesions with an indication that the lesion split from the specified lesion. In this case, appearance of a new lesion from a previous lesion that split will not be considered

disease progression solely due to appearance of a new lesion (may be considered disease progression due to > 25% increase in the sum of the products of the perpendicular diameters of all index tumors since baseline, or the unequivocal appearance of a new tumor, other than the product of the split tumor, since the last response assessment time point).

Measureable Tumor Assessment/Burden:

Baseline Documentation of “Index Lesions”:

All baseline evaluations should be performed as close as possible to randomization and never more than 4 weeks (ie, 28 days) prior to randomization.

At baseline, up to 10 measurable cutaneous, nodal, or soft tissue lesions will be chosen to measure over the course of therapy. The distribution of these index lesions should be representative of the subject’s overall disease status. Index lesions should be selected on the basis of their size (lesions with longest bi-dimensionally perpendicular diameters) and suitability for accurate repeated measurements by imaging techniques (CT, MRI or ultrasound) and/or other method such as clinical exam.

The sum of the products of the largest perpendicular diameters of all index lesions will be calculated and reported.

If a subject has multiple small superficial cutaneous melanoma lesions at baseline (each lesions is less than 10 mm in at least 2 dimensions) which in aggregate have a total diameter of ≥ 10 mm in at least 2 dimensions, up to 10 largest lesions that were included in this measurement will be reported as “Index Lesions”, and the sum of the products of the two largest perpendicular diameters of these lesions will be calculated and reported for tumor response assessments.

Baseline Documentation of “Nonindex Lesions”:

All other lesions (or sites of disease), including any measurable lesions that were not chosen as index lesions will be identified as nonindex lesions. Nonindex lesions should be recorded and assessed qualitatively over the course of therapy.

Follow-up “Index Lesions”:

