#### **4.1.2 Secondary Endpoint**

##### **4.1.2.1 Efficacy Endpoints**

##### **4.1.2.1.1 Tumor Response (Arm 1 Only)**

The overall tumor response is evaluated up to the earlier of surgical resection or subsequent anti-cancer therapy. Lesion-level response is evaluated up to the earliest event of start of subsequent anti-cancer therapy, merge with another lesion, or resection. Subject-level response is evaluated up to the earliest event of start of subsequent anti-cancer therapy or a partial or complete lesion resection.

Following endpoints will be analyzed for tumor response analysis,

- The overall tumor response is per the modified WHO criteria of tumor.
- Tumor response in injected/uninjected lesion(s)
  - The subject-level injected and uninjected responses will be based on the tumor burden of only injected index lesions including injected new measurable lesions, or the tumor burden of only uninjected index lesions including uninjected new measurable lesions, respectively.
  - The lesion-level injected and uninjected response will evaluate the change of the area of each individual lesion.
- Similar to tumor response in injected/uninjected lesions, lesion-level and subject-level response may also be conducted for lesion subtypes, eg, cutaneous / subcutaneous, nodal.

For the subject-level tumor response by tumor burden type (injected, uninjected lesions), a response is achieved if the percentage of the specific tumor burden type reduction from baseline for both baseline and new measurable lesions (if applicable) is at least 50%. Overall tumor burden is calculated at a visit as the sum of tumor areas of all lesions of the same type. The incidence of subject-level tumor response will be reported as the proportion of subjects with an evaluable tumor burden of the corresponding type that achieves a response.

The incidence of lesion-level response will be reported as the proportion of evaluable lesions in response. A lesion is in response if the decrease in tumor area is  $\geq 50\%$ .

All overall tumor burden and lesion response analyses will be based on bi-dimensional lesion measurements reported at a tumor assessment and will not consider injected lesion longest diameters reported at the time of investigational product administration forms.

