**Table 2. Study Design Characteristics Example Endpoint Summary Table**

Endpoint	Primary Summary and Analysis Method	Sensitivity Analysis
Key Secondary Endpoints		

 
• Rate of R0 surgical resection;
 
• Rate of pCR
 
	
 
• 80% exact CI by randomized treatment arm in the ITT analysis set per Clopper-Pearson.
 
• 80% approximate exact CI for the between-arm difference per Wilson's score method with continuity correction.
 
	
 
• Repeat using the efficacy analysis set, if necessary.
 
• Multivariate logistic models may be used to explore the prognostic and/or predictive value of baseline factors.
 

Tumor response (Arm 1 Only): 
 
• Overall Tumor Response (per Investigator)
 
• Individual injected lesion response overall and by subtype (cutaneous / subcutaneous vs lymph node)
 
• Individual uninjected lesion response overall and by subtype (cutaneous / subcutaneous vs lymph node)
 
• Subject response on overall injected lesions
 
• Subject response on overall uninjected lesions
 
	
 
• For response rate use the Clopper-Pearson method to calculate exact 80% CIs;
 
• For time to response the Kaplan-Meier (K-M) estimate
 
• The tumor response analysis is performed in the ITT analysis set.
 
	
 
• Repeat using the efficacy analysis set, if necessary.
 

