**(adjuvant systemic therapy with or without radiotherapy vs radiotherapy without adjuvant systemic therapy vs none).**

Multivariate proportional hazards models may be used to explore the prognostic and/or predictive value of baseline factors.

The Clopper-Pearson method ([Clopper and Pearson, 1934](#)) will be used to calculate exact CIs for binary endpoints (eg, overall tumor response, response in injected and uninjected lesions, R0 rate, pCR) (see [Section B.1](#) for SAS code fragments). Wilson's score method with continuity correction ([Newcombe, 1998](#)) will be used to calculate an approximate exact CI for between-group differences in binary rates (see [Section B.4](#) for SAS code fragments). Multivariate logistic models may be used to explore the prognostic and/or predictive value of baseline factors.

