## Appendix B. Technical Detail and Supplemental Information Regarding Statistical Procedures and Programs

### Code Fragments

#### B.1 Exact Confidence Interval

```
proc freq data=dat1;  
  tables R0/ binomial(exact) alpha=.2;  
  by TRTGRP;  
run;
```

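### The 80% Clopper-Pearson intervals for individual-lesion response ignore clustering of lesions within subjects; they are too narrow if a subject's lesions tend to respond together, by an amount the documents do not fix

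*SAP*

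**What the plan says.** SAP section 4.1.2.1.1 makes the lesion the unit of the lesion-level rate: "The incidence of lesion-level response will be reported as the proportion of evaluable lesions in response". SAP Table 2 lists "Individual injected lesion response overall and by subtype (cutaneous / subcutaneous vs lymph node" and "Individual uninjected lesion response overall and by subtype (cutaneous / subcutaneous vs lymph node" in the same row as overall response and subject-level injected and uninjected response. One rule serves the whole row: "For response rate use the Clopper-Pearson method to calculate exact 80% CIs". SAP section 10.5.2 repeats it, applying Clopper-Pearson to give "exact CIs for binary endpoints (eg, overall tumor response, response in injected and uninjected lesions, R0 rate, pCR", and Protocol section 10.5.3 says the same. The code in SAP Appendix B.1 is a plain binomial call, "tables R0/ binomial(exact) alpha=.2", with no subject identifier.

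A subject can contribute several lesions. Protocol Appendix D states: "At baseline, up to 10 measurable cutaneous, nodal, or soft tissue lesions will be chosen to measure over the course of therapy". SAP section 6 also counts new measurable lesions as evaluable. Neither document gives a cluster bootstrap, a GEE (generalized estimating equations) model, a design effect or any other within-subject adjustment for lesion response. The only repeated-subject statement is in the IPCW code (Appendix B.10), which concerns adjuvant therapy.

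**The concern.** Clopper-Pearson guarantees its coverage only for independent Bernoulli outcomes. Lesions in one subject share a host and an immune system. The trial's own rationale (Protocol 2.2 and 2.3) relies on a systemic immune response, so positive correlation between a subject's lesions is plausible. If it is present, the pooled lesions carry less information than their number suggests, and the interval is too short.

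Response in injected and uninjected lesions is a secondary objective. The trial tests no formal hypothesis, so estimates and intervals are what it delivers. Under SAP 10.1, tumor response has its primary analysis on the second-interim data, so these intervals may be reported early. An interval labelled as exact 80% would then overstate how precisely the lesion-level rates are known.

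**Working it through.** **Inputs from the documents**
- Arm 1 size: 150 randomized 1:1, so about 75 subjects (Protocol 3.1, 3.3).
- Interval: Clopper-Pearson, two-sided 80%, z = 1.2816.
- Illustrative response rates, from the earlier phase 3 study in Protocol 2.2: injected 47% + 17% = 64%; uninjected non-visceral 22% + 12% = 34%.

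**Inputs that are assumed.** The documents give neither mean lesions per subject (m) nor the ICC for this trial. Ten is a cap on index lesions, and one lesion is enough for entry (Protocol 4.1.1). Ranges are therefore shown. The plan states no expected lesion-level rate or interval, so there is no figure to reproduce.

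**Step 1: design effect.** DE = 1 + (m_w - 1) x ICC, where m_w = sum(m²)/sum(m), which equals m when all counts are equal. The interval should be about √DE times as wide.
- m = 2, ICC 0.1: DE = 1.1, √DE = 1.05
- m = 3, ICC 0.3: DE = 1.6, √DE = 1.26
- m = 4, ICC 0.4: DE = 2.2, √DE = 1.48
- m = 8, ICC 0.5: DE = 4.5, √DE = 2.12

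**Step 2: coverage by hand.** Coverage ≈ 2Φ(1.2816/√DE) - 1.
- m = 3, ICC 0.3: 1.2816/1.265 = 1.013, coverage 0.69
- m = 4, ICC 0.4: 1.2816/1.483 = 0.864, coverage 0.61
- m = 8, ICC 0.5: 1.2816/2.121 = 0.604, coverage 0.45

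This leaves out the built-in conservatism of Clopper-Pearson, which raises actual coverage a little when lesions are few.

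**Step 3: coverage by simulation.** Beta-binomial lesions, 75 subjects, near-equal lesion counts, 80% Clopper-Pearson on the pooled lesions:

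| Lesions per subject | ICC | Injected (64%) | Uninjected (34%) |
|---|---|---|---|
| 1.5 | 0.1 | 0.82 | 0.82 |
| 1.5 | 0.3 | 0.79 | 0.79 |
| 2 | 0.1 | 0.83 | 0.78 |
| 2 | 0.3 | 0.79 | 0.74 |
| 3 | 0.1 | 0.77 | 0.80 |
| 3 | 0.3 | 0.71 | 0.73 |
| 5 | 0.3 | 0.64 | 0.62 |
| 10 | 0.3 | 0.51 | 0.52 |

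With 70 subjects and variable counts (1 + Poisson, capped at 10):
- mean 2, ICC 0.1: about 0.80
- mean 2, ICC 0.3: 0.74-0.75
- mean 4, ICC 0.4: 0.60-0.61 (interval should be 1.5 times as wide)
- mean 8, ICC 0.5: 0.45-0.47 (2.1 times as wide)

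At ICC 0 coverage is 0.81-0.83, so the loss comes from clustering. Uneven counts make it worse: with a mean of 3.1 lesions, range 1-10 and a coefficient of variation of about 1, coverage at ICC 0.3 is 0.58-0.59.

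**Step 4: one interval worked through.** Take m = 3, so 75 x 3 = 225 lesions, of which 144 respond (64%). The planned 80% interval is 0.596-0.682. Using Clopper-Pearson with 225/DE instead:
- ICC 0.1: 225/1.2 = 187.5, giving 0.591-0.686
- ICC 0.3: 225/1.6 = 140.6, giving 0.583-0.694
- ICC 0.5: 225/2.0 = 112.5, giving 0.576-0.700

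Counting only subjects (48 of 75) gives 0.560-0.714 as a conservative bound.

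**The case against.** The strongest reply is that little depends on these intervals. All analyses are descriptive, lesion response is an Arm 1-only summary, the point estimates do not change, and no decision rule uses the interval. The same table plans subject-level injected and uninjected response, for which Clopper-Pearson is right, and the objective in Protocol 1.2 does not name the lesion as the unit. All of this stands, and it limits the severity.

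The size is also open to challenge. Protocol 2.2 reports "3,916 measurable lesions (average 13) in 285 subjects", but those subjects had unresectable disease and the lesions included visceral ones. That count does not predict a completely resectable population. Protocol 6.2.1.1 asks for all reasonably injectable lesions to be injected, so uninjected lesions may come from few subjects. With 25 contributing subjects and 1.5 lesions each, coverage at ICC 0.3 is about 0.80-0.81. It falls to 0.76 at 2 lesions and 0.71 at 3.

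A reader might infer that these intervals are known to cover far less than 80%. The documents do not support that, because it depends on an ICC and a lesion count that they do not give. A reader might also infer that every tumor-response interval in Table 2 is invalid, or that evidence on uninjected disease rests on the lesion-level rate alone. Neither follows: the other rates use one outcome per subject, and the subject-level uninjected rate addresses the same question with a valid interval.

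None of this removes the defect. The written rule treats a subject's lesions as independent, and nothing elsewhere in the plan corrects it.

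**Conclusion.** Wrong as written, and it should be fixed, but it does not threaten the trial's main conclusions. For any positive ICC with more than one lesion per subject, the planned interval is narrower than the clustered data justify. Whether that matters in practice depends on assumed values. Coverage stays near 80% with about 1.5 lesions per subject, or with 2 lesions at ICC 0.1. It is about 70-75% with 2-3 lesions at ICC 0.3, although one case (exactly two injected lesions each) still gives 0.79. It is about 45-60% with 4-8 lesions at ICC 0.4-0.5. The point is confined to individual-lesion rates and their subtype splits. Overall response, subject-level injected and uninjected response, R0, pCR, RFS and the sample size are unaffected.

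**What to change.** Amend SAP Table 2 and section 10.5.2 for individual-lesion rates only (injected, uninjected and by subtype):

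- Keep the pooled proportion of SAP 4.1.2.1.1 as the estimate.
- Compute the 80% interval by a subject-level cluster bootstrap: resample subjects with all their lesions, at least 2000 replicates. A GEE model with independence working correlation and robust standard error clustered on subject is an equivalent choice, and it preserves the pooled proportion. An exchangeable working correlation would reweight subjects and change the estimate. Name one method in advance.
- Do not reuse the Appendix B.3 code unchanged. It draws 100 replicates and resamples rows, which in a lesion data set would be lesions.
- Set a fallback for cells with 0% or 100% response, where the bootstrap collapses to zero width and the logistic model has no finite estimate, and for cells with very few subjects. SAP 4.2 already uses fewer than 20 subjects as an example of too small. There, use Clopper-Pearson with an effective sample size: lesions divided by the design effect or, conservatively, the number of contributing subjects. A 0% or 100% cell cannot supply its own design effect, so say where it comes from.
- Report the number of contributing subjects and the distribution of lesions per subject beside each rate.
- Keep Clopper-Pearson wherever each subject gives one outcome.

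The cost is a short SAP change, a short extra program and somewhat wider lesion-level intervals. No new data are needed.

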 - Arm 1: day 1 of week 12 (\pm 2 weeks) or within 1 week prior to surgery if a subject ends talimogene laherparepvec prior to week 12
- Response assessment per modified WHO response criteria ([Appendix D](#))
 - Arm 1: day 1 of week 12 (\pm 2 weeks) or within 2 weeks prior to surgery if a subject ends talimogene laherparepvec prior to week 12
- Histological tumor assessment of the surgical specimens. Surgical specimens will be assessed for presence of viable tumor and tumor margin status for cutaneous and subcutaneous tumor.
 - Tumor-free margins (negative margins, R0) resection is defined by pathologist as absence of ink on the tumor. All other resections of viable tumor are described as tumor positive margins resections, and are defined as
 - R1 resection - complete resection with no grossly visible tumor left behind as defined by the surgeon, or
 - R2 resection - partial resection with grossly visible tumor left behind as defined by the surgeon.
 - A pathological complete response (pCR) in Arm 1 is defined as no evidence of viable tumor cells on complete pathological evaluation of the surgical specimen per institutional standards of care
- Recording of adverse events at each visit
- Recording of serious adverse events at each visit. Serious adverse events will be reported to Amgen within 24 hours following the investigator's knowledge of the event

- Documentation of concomitant medications at each visit
- Arm 1 - Reporting pregnancy in a female subject or a female partner of a male subject while the subject is taking talimogene laherparepvec treatment and through 3 months after end of treatment ([Section 9.3](#))
- Arm 1 - Reporting lactation case in a female subject while the subject is taking talimogene laherparepvec treatment and through 3 months after end of treatment ([Section 9.3](#))
- Talimogene laherparepvec administration
 - Arm 1: day 1 of weeks 1, 4, 6, 8, 10, and 12 or until all injectable tumors have disappeared, intolerance of study treatment, whichever occurs first. Subjects who experience growth in existing tumors or the appearance of new tumors will be allowed to remain on talimogene laherparepvec treatment until week 12 of therapy unless, in the opinion of the investigator and in consultation with the sponsor's medical monitor, immediate surgical resection or any other treatment for melanoma is warranted.
- Surgery

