 - Arm 1: For subjects who complete 12 weeks of talimogene laherparepvec treatment, surgical resection of melanoma lesion(s) will be performed at any time during weeks 13 to 18. Subjects who stop talimogene laherparepvec prior to week 12 due to disappearance of all injectable tumor lesions, intolerance to talimogene laherparepvec, or any other reason will undergo surgical resection of melanoma lesion(s) or tissue where melanoma was present before CR within 1 to 6 weeks after the last dose of talimogene laherparepvec. Refer to [Appendix F](#) for surgery guidelines.
 - Arm 2: Surgical resection of melanoma tumor lesion(s) will be performed after randomization any time during weeks 1 to 6. Refer to [Appendix F](#) for surgery guidelines.

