### 3.2 Sample Size

All analyses will be descriptive with no formal hypothesis testing. The primary objective of the study is to estimate the treatment effect, as measured by the hazard ratio of RFS, of talimogene laherparepvec neoadjuvant therapy followed by surgery (Arm 1) compared to surgery alone (Arm 2) in subjects with resectable, stage IIIB to IVM1a melanoma. Approximately 150 subjects will be randomized 1:1 to receive Arm 1 vs Arm 2 stratified by: (i) disease stage (IIIB nodal vs IIIB in-transit vs IIIC nodal vs IIIC in-transit with nodal vs IVM1a), and (ii) planned adjuvant therapy (adjuvant systemic therapy [eg, INF $\alpha$ , ipilimumab] with or without radiotherapy vs radiotherapy without adjuvant systemic therapy vs none). Primary efficacy analysis of RFS will be based on the Intent to Treat Analysis Set. An overall between-group difference in RFS will be evaluated with a log-rank test and corresponding proportional hazards model without stratification. The Kaplan-Meier (KM) method will be used to estimate 1-year, 2-year, 3-year, 5-year, and overall RFS. Subjects who are not confirmed to be disease-free post-surgery (i.e., who do not have an R0 surgical outcome) or who withdraw prior to surgery will be considered a failure at randomization for RFS, RRFS, LRFS and DMFS. The primary analysis for the primary endpoint will occur at the later time of either the occurrence of approximately 64 events (local, regional, or distant recurrence of melanoma or death) or approximately 2 years after the end of randomization. An 80% CI will be estimated for the hazard ratio of RFS. In addition, an 80% CI will also be estimated for the between-arm difference (Arm 1 – Arm 2) in 2-year RFS, i.e.,  $\Delta$  2-year RFS. It is assumed that: (i) RFS is exponential over the first 2 years, (ii) the 2-year RFS for Arm 2 is about 0.60 (Eggermont et al, 2008), and that there will be a 10% exponential probability of drop-out by the primary analysis. Simulations were performed for various scenarios from 0.05 to 0.15 to evaluate the following parameters assuming possible true  $\Delta$  2-year RFS values of 0.10, 0.125, and 0.15: (i) the average  $\Delta$  2-year RFS 80% CI and its width, (ii) the probability that the  $\Delta$  2-year RFS 80% CI is above 0, and (iii) the average number of events at the

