Pathological Complete Response (pCR) is defined as no evidence of viable tumor cells on complete pathological evaluation of the surgical specimen per institutional standards of care. pCR rate is defined as proportion of subjects which achieves a pCR. For each subject, the pCR status (pCR or non-pCR) will be determined based on whether or not viable tumor was detected in the surgical specimen.

- Last Valid Tumor Evaluation

For overall tumor response per modified WHO response criteria the last valid tumor evaluation refers to the last valid tumor response assessment (PR, CR, SD or PD) per investigator. For the subject-level tumor response based on the tumor burden of a subset of lesions (injected, uninjected lesions, or other subtype) or the lesion-level response the last valid tumor evaluation refers to the assessment where the corresponding tumor burden or the corresponding individual tumor area is not missing.

- Baseline Lesion

Lesions measured at the most recent visit on or before receiving the first administration of talimogene laherparepvec (i.e., study day 1) will be flagged as baseline lesions. Baseline lesions must have positive tumor area. Lesions reported in the baseline measurable lesion CRF page but with a tumor area of zero or missing value at the last measurement on or before study day 1 will not be considered baseline lesions.

- New Lesion

New lesions are those that first appear after study day 1 with a positive tumor area or lesions without a positive lesion area in the last assessment on or before study day 1

but a positive lesion area from follow up tumor measurements. Baseline tumor area of a new lesion is obtained from the earliest date with positive bi-dimensional tumor measurements after study day 1. If a new lesion(s) that appears in between scheduled tumor response assessments disappear(s) before the next scheduled assessment, there is no need to include this lesion for tumor response evaluation

- Evaluable Lesion

A baseline or new measurable lesion is defined as evaluable if it has an initial positive area followed by at least 1 assessment with a non-missing area.

- Injected/Uninjected Lesion

Baseline or new lesions that are reported as injected with talimogene laherparepvec at any time during the treatment period are considered injected lesions. Baseline or new lesions that are not reported as injected with talimogene laherparepvec are considered uninjected lesions.

- Baseline Tumor Burden

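### Kaplan-Meier is prescribed for Arm 1 time to response with one scheduled assessment before surgery and no censoring rule, so the end of the curve can overstate response

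*SAP*

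**What the plan says.** SAP Table 2 (Section 10.5), in the Arm 1 tumor response row, gives three instructions. The rate: "For response rate use the Clopper-Pearson method to calculate exact 80% CIs". The timing: "For time to response the Kaplan-Meier (K-M) estimate". The population: "The tumor response analysis is performed in the ITT analysis set". The row states neither a time origin nor a censoring date for the timing analysis.

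Protocol Section 7.2.2 places the response assessment at "Arm 1: day 1 of week 12", with a window of 2 weeks either side, "or within 2 weeks prior to surgery if a subject ends talimogene laherparepvec prior to week 12". The Arm 1 schedule of assessments shows no other response assessment between baseline and surgery. For those who complete treatment, "surgical resection of melanoma lesion(s) will be performed at any time during weeks 13 to 18". SAP Section 4.1.2.1.1 ends evaluation of overall response at surgery or at the start of subsequent anticancer therapy, whichever is earlier. Protocol Appendix D requires no confirmation of response, so one visit settles each subject's status.

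SAP Section 9.3.1 refers missing-data handling to the endpoint definitions in Section 4, which contain no rule for time to response. SAP Section 6 does define a relevant date: for overall response, "the last valid tumor evaluation refers to the last valid tumor response assessment (PR, CR, SD or PD) per investigator". SAP Sections 4.1.1 and 4.1.2.1.2 use the last valid tumor evaluation as the censoring date for RFS, LRFS, RRFS and DMFS. Nothing applies it to time to response.

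**The concern.** Kaplan-Meier treats a censored subject as someone who could still have the event later, at the rate seen in those who remain at risk. Here a non-responder is seen once and then operated on, and evaluation stops. No later response can be recorded.

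If the non-responder leaves the risk set on the very visit that would have shown a response, the risk set shrinks across the visit window while each day's visitors keep responding at the same rate. The curve then climbs past the proportion who respond. At stake is a response curve, and any median read from it, that reflects how visits were scheduled and sits beside a much lower response rate in the same table row.

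**Working it through.** The documents give no expected response rate and no figure for time to response, so there is nothing of the plan's own to reproduce on this point.

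**Inputs from the documents**
- Arm 1 size: "Approximately 150 subjects will be randomized 1:1 to receive Arm 1 vs Arm 2 stratified by" two factors, so 150 / 2 = 75.
- Assessment: day 1 of week 12 is study day 11 × 7 + 1 = 78. With ± 14 days this is days 64 to 92, or 29 calendar days.
- Surgery: weeks 13 to 18, days 85 to 126.

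**Assumptions**
- True response rate p = 30%, checked from 10% to 50%.
- The spread of visit dates, and the proportion who stop early.

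**Reading A: non-responders censored at their assessment.** Spread the subjects evenly over m visit days with a fraction p responding each day. When k day-groups remain at risk, counting today's, the Kaplan-Meier factor is 1 − p/k. The curve therefore ends at

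1 − ∏ (1 − p/k), k = 1 to m.

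With p = 0.30:
- m = 1 (all on one day): 1 − 0.70 = 30%.
- m = 2: 1 − 0.85 × 0.70 = 40.5%.
- m = 7 (± 3 days): 1 − 0.423 = 58%.
- m = 15 (± 7 days): 1 − 0.340 = 66%.
- m = 29 (± 14 days): 1 − 0.280 = 72%.
- m = 75 (no ties): 1 − 0.211 = 79%.

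Simulation with random integer visit days (3,000 trials of 75 subjects) agrees: 58%, 66% and 71–72% for the three windows. Dates clustered normally around day 78 give 73% (SD 3 days) to 76% (SD 5 days). Other true rates over the full window:

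| True rate | End of curve |
|---|---|
| 10% | 33% |
| 20% | 56% |
| 30% | 72% |
| 40% | 82% |
| 50% | 89% |

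The excess builds up late. At a true 30% over the full window, the curve averages 19% on day 78 and 47% while at least 10 subjects remain at risk. It crosses 50%, which yields a finite median, in about 92–93% of trials.

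**Reading B: non-responders censored at surgery**, uniform over days 85 to 126 and never before the assessment. Nearly all non-responders are still at risk when the responders have their events, so the curve ends at 30.6% for a true 30%, 10.2% for 10% and 51% for 50%. If an assumed 20–30% stop early and have surgery on days 30 to 84, it ends at about 35–37% for a true 30%.

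**The case against.** The strongest answer is that the large figures depend on a censoring rule the SAP does not state for this endpoint. Where the SAP wants censoring at the last valid evaluation, it says so. For response, the boundary it names is surgery or subsequent therapy, and under that reading the distortion is small. The 72% is the sparse end of the curve, and the rates and date spreads are assumed. SAP Section 10.5.2 does not list time to response among the endpoints for which quartiles are planned. Protocol Section 10.1.1.2 makes related endpoints such as this one optional, to be evaluated if appropriate, and no decision or between-arm comparison depends on it.

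Most of this stands. A reader might infer that Kaplan-Meier with a single assessment must carry the curve toward 1 whatever the true rate, or that the plan will show 72% for a true 30%. The documents do not support either inference: the large excess needs both censoring at the visit and visits on different days, and even then a true 10% ends at about 33%. Nor is the reported response rate biased.

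What does not stand is the suggestion that this is only a missing detail. The SAP defines a last valid evaluation specifically for overall, subject-level and lesion-level response. A response rate needs no such date, and the date's use elsewhere in the SAP is for censoring. Reading A is therefore the one a programmer would most likely choose. Reading B also overshoots once some subjects have early surgery.

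**Conclusion.** The point holds in a limited form. The prescribed method does not suit data in which each subject is assessed once and then leaves evaluation, and the SAP leaves open the rule that determines how far the result departs from the response rate. For an assumed true 30% and 75 subjects, the end of the curve is about 58–72% for windows from ± 3 to ± 14 days under censoring at the assessment, and 30% only if everyone is assessed on the same study day. Under censoring at surgery it is about 31%, or about 35–37% with an assumed 20–30% stopping early. The Clopper-Pearson rate is untouched and the endpoint is descriptive and optional, so the correction is minor.

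**What to change.** In the tumor response row of SAP Table 2, replace the Kaplan-Meier line with one of two options:

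- A cumulative incidence curve for first response, with surgery without response, subsequent anticancer therapy, and withdrawal or death before response as competing ends. Once every Arm 1 subject has reached one of these ends, the curve finishes at the observed response proportion.
- The median and range of time to response among responders only, labelled as such, beside the ITT response proportion and its exact 80% interval.

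State the time origin in the same line. The SAP already plans cumulative incidence methods for LRFS in Section 10.5.2, so the first option needs no new technique. Stating surgery as the censoring date while keeping Kaplan-Meier would remove most of the excess, but not the part due to early surgery. The cost is one table line and slightly different programming, with no change to data collection.
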